## **Appendix 8. Pandemic Risk Assessment and Mitigation Plan**

During an ongoing pandemic, potential risks associated with subjects being unable to attend study visits have been identified for this study.

These risks can be summarized as follows:

### 1) Study drug supplies to subjects and sites:

- a) Subjects may be unable to return to the site for a number of visits to get the study drug, or the site may be unable to accept any subject visits. Without study drugs, the subject would not be able to stay on the study drug as planned per protocol.

Mitigation plan: Study drug supplies may be provided to the subject from the site without a clinic visit, once it is confirmed that the subject may safely continue on study drug as determined by the principal investigator (PI). A virtual study visit, via phone or video conferencing, must be performed prior to remote study drug resupply. At the earliest opportunity, the site will schedule in-person subject visits and return to the protocol's regular schedule of assessments. A qualified courier may be utilized to ship the study drug from sites to study subjects if permitted by local ethic committee (EC)/institutional review boards (IRB)/Regulatory Authority as applicable and with sponsor's approval.

- b) Shipments of study drug could be delayed because of transportation issues. Without study drug subject would not be able to stay on the study drug as planned per protocol.

Mitigation plan: The sites' study drug inventory should be closely monitored. Site staff should notify the sponsor or delegate if they foresee shortage in study drug inventory or if there is any interruption in local shipping service. The sponsor will continue to monitor inventory at the study drug depot and study sites. Manual shipments will be triggered as necessary.

### 2) Subject safety monitoring and follow up:

- a) Subjects may be unable or unwilling to come to the study site for their scheduled study visits as required per protocol.

Mitigation plan: For subjects who may be unable or unwilling to visit the study site for their scheduled study visits as required per protocol, the PI or qualified delegate will conduct a virtual study visit, via phone or video conferencing, to assess the subject within target visit window date whenever possible. During the virtual study visit, the following information at minimum will be reviewed:

- i) Confirm if subject has experienced any adverse events (AEs)/serious adverse events (SAEs)/special situations (including pregnancy) and follow up on any unresolved AE/SAEs.

- ii) Review current list of concomitant medications and document any new concomitant medications.
- iii) If applicable, confirm subjects study drug supply is sufficient to last until the next planned visit date. If study drug resupply is needed it will be provided as described above in (1).
- iv) If applicable, remind subject to maintain current dosing and to keep all dispensed study drug kits for return at the next on-site visit.

- b) Subjects may be unable or unwilling to travel to the site for planned assessments (eg, safety blood draws); hence samples may not be sent for central lab analyses.

Mitigation plan: Local labs may be utilized as appropriate to monitor subject safety until the subject can return to the site for their regular follow up per protocol. Any laboratory assessments conducted at a local lab due to the pandemic will be documented accordingly. Pregnancy testing may be performed using a home urine pregnancy test if local lab pregnancy testing is not feasible.

- c) Subjects may be unable or unwilling to attend the study visit to sign an updated informed consent form (ICF) version.

Mitigation plan: The site staff will follow their approved consent process and remain in compliance with local EC/IRB and national laws and regulations. Remote consent will be allowed if has been approved by the local EC/IRB. The consent process will be documented and confirmed by normal consent procedure at the earliest opportunity.

3) Protocol and monitoring compliance:

- a) Protocol deviations may occur, in case scheduled visits cannot occur as planned per protocol.

Mitigation plan: If it is not possible to complete a required procedure, an unscheduled visit should be conducted as soon as possible when conditions allow. The situation should be recorded and explained as a protocol deviation. Any missed subject visits or deviation to the protocol due to the pandemic must be reported in the eCRF and described in the clinical study report (CSR). Any virtual study visits that are conducted in lieu of clinic visits due to the pandemic will be documented as a protocol deviation related to the pandemic.

- b) Monitors may be unable to carry out source data review (SDR) or source data verification (SDV), or study drug accountability or assess protocol and GCP compliance. This may lead to delays in SDV, an increase in protocol deviations, or under reporting of AEs.

Mitigation plan: The study monitor is to remain in close communication with the site to ensure data entry and query resolution. The study monitor is to reference the Study Monitoring Plan for guidance on how to conduct a remote monitoring visit. The study staff is to save and document all relevant communication in the study files. The status of sites that cannot accept monitoring visits and/or subjects on site, must be tracked centrally and updated on a regular basis.

4) Missing data and data integrity:

- a) There may be an increased amount of missing data due to subjects missing visits/assessments. This could have an impact on the analysis and the interpretation of clinical trial data.

Mitigation plan: Implications of a pandemic on methodological aspects for the study will be thoroughly assessed and documented, and relevant actions will be taken as appropriate (ie, modification of the statistical analysis plan) and in compliance with Regulatory Authorities' guidance. Overall, the CSR will describe the impact of the pandemic on the interpretability of study data.

Risks will be assessed continuously, and temporary measures will be implemented to mitigate these risks as part of a mitigation plan, as described above. These measures will be communicated to the relevant stakeholders as appropriate and are intended to provide alternate methods that will ensure the evaluation and assessment of the safety of subjects who are enrolled in this study.

Since these potential risks are considered mitigated with the implementation of these measures, the expected benefit-risk assessment of GS-4224 in study subjects remains unchanged.

CL_{ss}/F	apparent oral clearance after administration of the drug: at steady state: $CL_{ss}/F = \text{Dose}/AUC_{tau}$, where “Dose” is the dose of the drug
$t_{1/2}$	estimate of the terminal elimination half-life of the drug, calculated by dividing the natural log of 2 by the terminal elimination rate constant (λ_z)
T_{last}	time (observed time point) of C_{last}
T_{max}	time (observed time point) of C_{max}
λ_z	terminal elimination rate constant, estimated by linear regression of the terminal elimination phase of the concentration of drug versus time curve

1. INTRODUCTION

This statistical analysis plan (SAP) describes the statistical analysis methods and data presentations to be used in tables, figures, and listings (TFLs) in the clinical study report (CSR) for Study GS-US-494-5484. This SAP is based on the study protocol amendment 5.0 dated 02 October 2020 and the electronic case report form (eCRF). The SAP will be finalized before database finalization. Any changes made after the finalization of the SAP will be documented in the CSR.

The study was originally designed to evaluate the safety, tolerability, Pharmacokinetics (PK), and efficacy of GS-4224 monotherapy in 2 stages: (1) Phase 1b dose-escalation in advanced solid tumors; and (2) Phase 2 dose expansion in select advanced solid tumors expressing ligand 1 of programmed cell death protein 1 (PD-L1) [tumor proportion score (TPS) \geq 1% or combined positive score (CPS) \geq 1 or \geq 10] or MSI-H cancers. The study was early terminated during Phase 1b dose escalation part due to lack of objective clinical efficacy in patients dosed in Phase 1b dose-escalation. The Phase 2 part of the study was not be initiated. Subjects currently on study will continue to be treated and/or followed until the end of study criteria are met. The SAP describes the analyses based on the Phase 1b data collected in the study only for a synoptic CSR.

1.1. Study Objectives

1.1.1. Primary Objectives

Phase 1b Dose Escalation

- To characterize the safety and tolerability of GS-4224 in subjects with advanced solid tumors
- To determine the maximum tolerated dose (MTD) or recommended Phase 2 dose (RP2D) of GS-4224 in subjects with advanced solid tumors

1.1.2. Secondary Objectives

Phase 1b Dose Escalation

- To evaluate the pharmacokinetics (PK) of GS-4224 in subjects with advanced solid tumors

Phase 2 Dose Expansion

- To evaluate the safety and tolerability of GS-4224 in subjects with advanced solid tumors

CCI

[REDACTED]

1.2. Study Design

GS-US-494-5484 is an open-label, multicenter, sequential dose-escalation and dose expansion study to evaluate the safety, tolerability, PK, and efficacy of GS-4224 in subjects with advanced solid tumors. The study will consist of 2 parts: the dose escalation portion, followed by dose expansion in subjects with tumors for which programmed cell death protein 1 (PD-1)/PD-L1 treatments are approved or are known to be active.

1.2.1. Dose Escalation (Phase 1b)

Subjects with advanced solid tumors who have failed or are intolerant to standard therapy or for whom no standard therapy exists will be sequentially enrolled at progressively higher dose levels of oral GS-4224 as monotherapy.

Dose escalation will proceed using a standard 3+3 design. The starting dose is 400 mg once daily (QD), with subsequent doses of 700 mg QD, 1000 mg QD, 1500 mg QD, and 1000 mg twice daily (BID). Dose level increases are 3-fold or less.

Dose Level Schema	
GS-4224 (mg)	Fold Increase
400 QD	-
700 QD	$\leq 3\times$
1000 QD	$\leq 3\times$
1500 QD	$\leq 3\times$
1000 BID	$\leq 3\times$

In the 1000 mg BID dose cohort, at least 6 (as part of the initial 3+3 design) and up to an additional 14 subjects (for a total of 20 subjects) with locally advanced, inoperable or metastatic cancer expressing PD-L1 (tumor proportion score [TPS] $\geq 10\%$ or combined positive score [CPS] ≥ 10) and who have not previously been treated with anti-PD-1/L1 antibodies will be enrolled. The additional 14 subjects will not be enrolled at the 1000 mg BID dose level if the subject incidence of DLTs is > 1 in the first 6 subjects. If the subject incidence of DLTs is > 1 in the first 6 subjects at 1000 mg BID, then 20 additional subjects with locally advanced, inoperable or metastatic cancer expressing PD-L1 [TPS $\geq 10\%$ or CPS ≥ 10] and who have not previously been treated with anti-PD-1/L1 antibodies will enroll at the MTD.

The initial block of each dose consists of 3 subjects. Dose escalation may occur if no subjects experience DLTs during the first 21 days of study drug dosing. If 1 subject within the initial cohort of 3 subjects experiences a DLT during the first 21 days of study drug dosing, an additional 3 subjects will be enrolled at the same dose level. If no DLTs are observed in the additional 3 subjects, dose escalation will occur. If 2 or more of the 6 subjects experience DLTs within the first 21 days, dose de-escalation to an intermediate dose will occur. The MTD is the highest dose level with a subject incidence of DLTs during the first 21 days of study drug dosing of 0 or 1 out of 6. A minimum of 6 subjects need to be treated at a dose level before this dose level can be deemed as the MTD. A subject who is withdrawn from the study before the completion of the first 21 days for a reason other than a DLT will be replaced.

If 2 or more delayed DLT-type adverse events (AEs) are noted after the first 21 day observation period within a dose escalation cohort, further accrual at all sites will be held pending safety analysis of the event, and will be restarted only with Investigator and Sponsor approval.

The SRT will review safety and relevant clinical data and make the dose escalation/stay/de-escalation decision. Source Data Verification (SDV) is not required to be performed prior to SRT meetings, as there will be alternative quality control checks implemented. These checks will be described in the SRT Charter.

At dose levels equal to or below the MTD, up to 6 additional subjects per dose level with biopsy accessible, PD-L1-positive (TPS $\geq 10\%$ or CPS ≥ 10) tumor lesions may be enrolled in the Dose Escalation Biopsy Substudy to evaluate the tumor target occupancy of GS-4224 in posttreatment tumor biopsy samples. Up to a total of 12 subjects may be enrolled at one of the dose levels in the biopsy substudy. The biopsy substudy cohort may be opened once the dose level has been cleared by the SRT for safety.

1.3. Sample Size and Power

The sample size of the study will be determined based on the number of dose levels evaluated and the emerging GS-4224-related toxicities and efficacy. The study is planned to enroll approximately 120 subjects.

Approximately 44 subjects will be enrolled in the dose escalation phase (Phase 1b) and approximately 36 subjects will be enrolled in the Dose Escalation Biopsy Substudy (Phase 1b).

Approximately 40 subjects will be enrolled into the Dose Expansion Cohort B1.

2. PLANNED ANALYSIS

2.1. Interim Analysis

2.1.1. Analyses for Dose Escalation Decisions

To support dose escalation decision, safety data, including DLTs and other AEs will be listed and summarized, if appropriate. Supportive data including demographic, disease history, concomitant medication, and drug administration will be listed. The analysis will occur when all subjects enrolled in a dose level have been followed for at least 21 days after the first dose of GS-4224 or two DLTs have been observed, whichever is earlier.

2.1.2. Analyses for Dose Expansion Decisions

To support dose expansion decision, available and relevant clinical data from all subjects treated in the escalation phase may be listed and summarized, if appropriate. This analysis was originally planned in the study protocol; however, it will not be done due to study early termination.

2.1.3. Primary Analysis

The study primary analysis will be conducted when all enrolled subjects have discontinued the study or have been on treatment of GS-4224 for at least 48 weeks and completed response assessment of Week 48.

This analysis was originally planned in the study protocol; however, it will not be done due to study early termination.

2.2. Final Analysis

The final analysis will be performed after all subjects have completed or discontinued from the study, outstanding data queries have been resolved or adjudicated as unresolvable, and the data have been cleaned and finalized.

3. GENERAL CONSIDERATIONS FOR DATA ANALYSES

Analysis results will be presented using descriptive statistics. For categorical variables, the number and percentage of subjects in each category will be presented; for continuous variables, the number of subjects (n), mean, standard deviation (StD) or standard error (SE), median, first quartile (Q1), third quartile (Q3), minimum, and maximum will be presented.

By-subject listings will be presented for all subjects in the All Enrolled Analysis Set and sorted by dose cohort, subject ID number, visit date, and time (if applicable). Data collected on log forms, such as AEs, will be presented in chronological order within the subject. The cohort to which subjects were initially assigned will be used in the listings. Age, sex at birth, race, and ethnicity information for each subject will be presented in the listings, as space permits.

3.1. Analysis Sets

Analysis sets define which subjects are included in an analysis. Analysis sets and their definitions are provided in this section. The analysis set will be identified and included as a subtitle of each table, figure, and listing.

3.1.1. All Enrolled Analysis Set

The All Enrolled Analysis Set includes all subjects who received a study subject identification number in the study after screening.

The All Enrolled Analysis Set will be used for subject enrollment summary and for data listings, unless otherwise specified.

3.1.2. Full Analysis Set

The Full Analysis Set includes all subjects who received at least 1 dose of study treatment. It will be used in the analyses of efficacy endpoints.

3.1.3. Safety Analysis Set

The Safety Analysis Set includes all subjects who received at least 1 dose of study treatment, with treatment assignments designated according to the actual treatment received. This is the primary analysis set for the safety analyses as well as study treatment administration.

3.1.4. DLT-Evaluable Analysis Set

The DLT-Evaluable Analysis Set includes all subjects in the Safety Analysis Set who enroll to the dose escalation cohort (excluding the Dose Escalation Biopsy Substudy), complete $\geq 75\%$ of the prescribed study treatment (ie., at least 16 of 21 doses) and have safety assessments through the protocol specified DLT assessment window (first 21 days of study dosing, inclusive) or have experienced a DLT prior to the completion of first 21 days of study dosing. Safety assessment relevant to the DLT-Evaluable Analysis Set definition will include laboratory serum chemistry tests and hematology tests as specified in the protocol. Determination of the MTD will be based on the DLT-Evaluable Analysis Set.

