**Statistical Methods:**

The study primary analysis will be conducted when all enrolled subjects have discontinued the study or have been on treatment of GS-4224 for at least 48 weeks and completed response assessment of Week 48.

Analysis Data Set

The All Enrolled Analysis Set includes all subjects who received a study subject identification number in the study after screening.

The Full Analysis Set (FAS) includes all subjects who took at least 1 dose of study treatment. It will be used in the analyses of efficacy endpoints.

The Safety Analysis Set will include data from all subjects who receive at least 1 dose of study treatment, with treatment assignments designated according to the actual treatment received. This analysis set will be used in the analyses of safety variables as well as study treatment administration.

The DLT-Evaluable Analysis Set includes all subjects in the Safety Analysis Set who enroll to the dose escalation cohorts (up to the first 6 subjects in the 1000 mg BID dose escalation cohort; excluding the Dose Escalation Biopsy Substudy), complete  $\geq 75\%$  of the prescribed study treatment and have safety assessments through the protocol-specified DLT assessment window (first 21 days of study dosing, inclusive) or have experienced a DLT prior to the completion of first 21 days of study dosing. Safety assessment relevant to the DLT-Evaluable Analysis Set definition will include laboratory serum chemistry tests and hematology tests as specified in the protocol. Determination of the MTD will be based on the DLT-Evaluable Analysis Set.

The PK Analysis Set will include data from subjects in the Safety Analysis Set who have received the study drug and have at least 1 sample with detectable drug concentration.

An IRC may review radiographic data in order to provide independent evaluation of tumor status. Tumor response status and progression will be assessed by the IRC using RECIST v1.1 with modifications or Lugano 2014 response criteria for cHL.

Efficacy Analysis

In efficacy analysis, ORR will be evaluated by tumor type and treatment in FAS. Tumor types with less than 5 subjects enrolled will be pooled for ORR summary. Subjects who do not have sufficient baseline or on-study tumor assessment to characterize response will be counted as nonresponders. Estimates and the corresponding 95% CIs based on the Clopper-Pearson exact method will be provided.

---

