#### 8.3.1.4. DLT-Evaluable Analysis Set

The DLT-Evaluable Analysis Set includes all subjects in the Safety Analysis Set who enroll to the dose escalation cohorts (up to the first 6 subjects in the 1000 mg BID dose escalation cohort; CCI [REDACTED]), complete  $\geq 75\%$  of the prescribed study treatment and have safety assessments through the protocol-specified DLT assessment window (first 21 days of study dosing, inclusive) or have experienced a DLT prior to the completion of first 21 days of study dosing. Safety assessment relevant to the DLT-Evaluable Analysis Set definition will include laboratory serum chemistry tests and hematology tests as specified in the protocol. Determination of the MTD will be based on the DLT-Evaluable Analysis Set.

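### SAP 3.1.4 omits the protocol's six-subject limit on the DLT-Evaluable set at 1000 mg BID, so the reported DLT denominator there could be up to 20 instead of up to 6

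*SAP*

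**What the plan says.** The protocol defines the DLT-Evaluable set in the Synopsis (Statistical Methods) and again in Section 8.3.1.4. The Synopsis puts two limits in one parenthesis: "up to the first 6 subjects in the 1000 mg BID dose escalation cohort; excluding the Dose Escalation Biopsy Substudy". Section 8.3.1.4 repeats the first limit, and the text after it is redacted.

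SAP 3.1.4 follows the rest of that definition closely but has only the second limit: the set "includes all subjects in the Safety Analysis Set who enroll to the dose escalation cohort (excluding the Dose Escalation Biopsy Substudy". The SAP sentence carries no redaction mark, so blacked-out text does not explain the difference. The same section adds: "Determination of the MTD will be based on the DLT-Evaluable Analysis Set".

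SAP 1.2.1 describes at least 6 subjects at 1000 mg BID and "up to an additional 14 subjects (for a total of 20 subjects". To qualify as the MTD, a dose must be the top one tested that meets this condition: "subject incidence of DLTs during the first 21 days of study drug dosing of 0 or 1 out of 6".

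SAP 7.1.7 summarises Day 1 to 21 DLTs in the DLT-Evaluable set, and SAP 4.1 reports the size of that set by cohort. SAP 7.7 declares no changes from the protocol's safety analyses.

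**The concern.** DLT incidence is the primary endpoint (Protocol 3.1), and the DLT-Evaluable set supplies its denominator. A programmer working from SAP 3.1.4 would include every evaluable 1000 mg BID escalation subject. A reader of the report, told in SAP 7.7 that nothing has changed, would assume the protocol's limit applied.

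The SAP also does not fit together internally. It bases the MTD on a set that can hold 20 subjects at one dose level, but states the rule per 6 subjects. A result such as 2 DLTs in 20 subjects has no defined reading under that rule.

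**Working it through.** **Inputs.** There are four QD levels (400, 700, 1000 and 1500 mg) and one BID level (SAP 1.2.1), with up to 6 subjects per level under 3+3. The 1000 mg BID cohort may grow by 14, to 20. Planned numbers are 44 in escalation, 36 in the biopsy substudy and 40 in Cohort B1, about 120 in total (SAP 1.3). Neither document gives a true DLT rate, so 5%, 10% and 20% are assumed below.

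**Step 1: are subjects 7 to 20 escalation subjects?** SAP 1.3 states: "Approximately 44 subjects will be enrolled in the dose escalation phase (Phase 1b) and approximately 36 subjects" in the substudy. The count reproduces:
- 4 × 6 + 20 = 44
- 44 + 36 + 40 = 120

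The 44 is reached only if all 20 BID subjects count as escalation subjects, separately from the substudy. SAP 3.1.4 therefore admits subjects 7 to 20, provided they meet its treatment and assessment conditions.

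**Step 2: size of the set when 1000 mg BID is expanded (planned maxima).**

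| | Protocol | SAP 3.1.4 |
|---|---|---|
| 1000 mg BID | 6 | 20 |
| All five levels | 5 × 6 = 30 | 4 × 6 + 20 = 44 |

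The extra 14 would be 14/44 = 31.8% of the SAP's set.

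**Step 3: same data, two results.** Protocol 8.4 calls for exact binomial 95% intervals. For x events in n subjects, the lower limit is the 2.5% quantile of Beta(x, n − x + 1), or 0 if x = 0. The upper limit is the 97.5% quantile of Beta(x + 1, n − x).

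| 1000 mg BID data | Protocol set | SAP set |
|---|---|---|
| 1 DLT in first 6, 0 in next 14 | 1/6 = 16.7% (0.4 to 64.1) | 1/20 = 5.0% (0.1 to 24.9) |
| 0 in first 6, 2 in next 14 | 0/6 = 0% (0 to 45.9) | 2/20 = 10.0% (1.2 to 31.7) |

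The shift can go either way, so the omission does not consistently favour the drug.

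**Step 4: how often would the SAP's set give a count that the rule does not address?** The 14 enrol only if the first 6 show at most 1 DLT. At most 1 in 20 implies at most 1 in the first 6, so

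P(≥2 of 20 | ≤1 of 6) = [P(≤1 of 6) − P(≤1 of 20)] / P(≤1 of 6).

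| Assumed rate | P(≤1 of 6) | P(≤1 of 20) | P(≥2 of 20, given ≤1 of 6) |
|---|---|---|---|
| 5% | 0.967 | 0.736 | 0.24 |
| 10% | 0.886 | 0.392 | 0.56 |
| 20% | 0.655 | 0.069 | 0.89 |

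**Step 5: what does the limit leave out?** Subjects 7 to 20 would contribute 14p expected subjects with a Day 1 to 21 DLT: 0.7, 1.4 and 2.8 at the three rates. The chance of at least one is 1 − (1 − p)^14 = 0.51, 0.77 and 0.96. With the limit in place, neither summary in SAP 7.1.7 would count those events, because its Safety Analysis Set summary covers only events after Day 21.

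**The case against.** The strongest reply is that the effect may be nil. According to SAP 1, the study stopped during Phase 1b and only a synoptic report is planned. Actual 1000 mg BID enrolment is not given. With 6 or fewer subjects there, the two definitions select the same people. This stands as a limit on size, but the text still needs correcting.

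A reader might infer that the wider set could change dosing or produce a wrong MTD. The documents do not support that. SAP 1.2.1 makes the extra 14 conditional on the DLT count in the first 6, and Protocol 3.2.3 has the safety review team decide escalation and define the MTD. SAP 1.1.1 also words the objective as MTD or RP2D, so the report may not need an MTD statement. The effect is confined to the reported incidence and the reported size of the set.

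The SAP cites protocol amendment 5.0, and the version of the supplied protocol cannot be confirmed. That lowers certainty about a departure from the governing text, although the 1000 mg BID design agrees between Protocol 3.2.1 and SAP 1.2.1. It does not remove the mismatch between SAP 3.1.4 and the SAP's own MTD rule.

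Finally, events in subjects 7 to 20 would still appear in the Safety Analysis Set TEAE tables (SAP 7.1.6). That is correct, and it is why an added DLT line is optional.

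**Conclusion.** The point holds and is minor. SAP 3.1.4 omits a limit that the protocol states twice, does not declare the change, and leaves a set that does not fit the SAP's own MTD rule. At 1000 mg BID the denominator could be up to 20 instead of up to 6, which can move the reported incidence from 16.7% to 5.0%, or from 0% to 10.0%. These are illustrations. They assume the cohort was expanded in full and that every subject was evaluable. The contrast of 30 with 44 applies only to that case.

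Two wider readings are not supported:
- If 1000 mg BID fails, "then 20 additional subjects with locally advanced, inoperable or metastatic cancer expressing PD-L1" are to enrol at the MTD. A reader might count that as a further effect of the omission. It is not, because the protocol's limit names only 1000 mg BID, so both documents define the set alike in that branch.
- A reader might see the absence of biopsy-substudy subjects from the Day 1 to 21 DLT summary as a second error. Excluding them is the protocol's own rule, and the SAP follows it.

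**What to change.** Add the protocol's six-subject limit for 1000 mg BID to the parenthesis in SAP 3.1.4. State that the six are counted among evaluable subjects after replacement, because Protocol 4.1.2 replaces subjects who withdraw early without a DLT or take too few doses.

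If the wider set is intended, declare it in SAP 7.7 or the clinical study report, and state that the MTD rule uses only the first 6.

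Optionally, add one supportive line to SAP 7.1.7 giving Day 1 to 21 events that meet DLT criteria for all treated 1000 mg BID subjects, so that subjects 7 to 20 are not lost from DLT reporting.

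The cost is one clause, or one note in the report, a route that SAP 1 already provides for changes after finalisation. The optional line uses data already collected. Trial conduct is unaffected.

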7.1.7. Definition and Analysis of Dose Limiting Toxicity

Toxicity will be graded according CTCAE Version 5.0. A DLT is any toxicity specified in the study protocol occurring during the DLT assessment window (Day 1 through Day 21).

DLTs occurred within the 21-Day DLT observation period will be summarized by PT in descending order of total frequency for the DLT-Evaluable Analysis Set. Toxicities that meet the criteria of DLTs and occur beyond the first 21 days observation period (ie. DLT-type AEs) will also be summarized for the Safety Analysis Set by PT only in descending order of total frequency.

In addition, by-subject data listings will be provided by cohort and subject ID number in ascending order for the following:

- Dose Limiting Toxicities
- DLT-type AEs: toxicities that met the criteria of DLTs and occurred beyond the first 21 days observation period during study

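### The SAP's DLT-Evaluable set drops the protocol's first-six limit at 1000 mg BID, leaves no MTD rule for a larger set, and declares no deviation

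*SAP*

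**What the plan says.** **Protocol.** The DLT-Evaluable definition in the synopsis (Statistical Methods) carries two restrictions: "up to the first 6 subjects in the 1000 mg BID dose escalation cohort; excluding the Dose Escalation Biopsy Substudy". Section 8.3.1.4 repeats the first one legibly, "up to the first 6 subjects in the 1000 mg BID dose escalation cohort"; the text after it is blacked out. Both places base the MTD on this set.

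**SAP.** Section 3.1.4 keeps the biopsy-substudy exclusion, the 75% dosing condition, the 21-day window and the statement that the MTD rests on this set. Its inclusion wording is "who enroll to the dose escalation cohort (excluding the Dose Escalation Biopsy Substudy"), with no limit at 1000 mg BID. Section 1.2.1 plans at least 6 and up to 20 subjects at that level and defines the MTD as the highest level with a "subject incidence of DLTs during the first 21 days of study drug dosing of 0 or 1 out of 6". Section 7.1.7 uses the same set for the DLT table: "DLTs occurred within the 21-Day DLT observation period will be summarized by PT". Section 7.7 states that the protocol's safety analyses are followed without deviation.

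**Still in force after termination.** The SAP records that "The study was early terminated during Phase 1b dose escalation part due to lack of objective clinical efficacy" and cancels the dose-expansion and primary analyses. It keeps the final analysis and the primary objective "To determine the maximum tolerated dose (MTD) or recommended Phase 2 dose (RP2D) of GS-4224". DLT incidence is the protocol's only primary endpoint (3.1 and 8.1.2).

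**The concern.** 1000 mg BID is the one escalation level planned to grow well past a 3+3 block. The protocol's limit makes the analysis set match a rule that is written for six subjects. Without it, the SAP applies that rule to a set of up to 20 and does not say whether 0 or 1 out of 6 then means at most one DLT (a count) or at most one sixth of subjects (a proportion). Two programmers could report different MTD conclusions from the same data.

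The denominator for the primary endpoint at this level could also differ between protocol and SAP. A study report that relied on SAP 7.7 would not disclose this.

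**Working it through.** **Is the gap real?** The SAP sentence is complete, so redaction does not explain the omission. The SAP does mention the first 6 subjects in 1.2.1, but only as the condition for enrolling the additional 14. It does not use that phrase to define the analysis set.

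**Inputs**
- Planned 1000 mg BID cohort (SAP 1.2.1): 6 + 14 = 20. This also fits the planned Phase 1b escalation total of 44, since four QD levels × 6 + 20 = 44 (the breakdown is inferred).
- Condition for enrolling the additional 14 (SAP 1.2.1): no more than 1 DLT in the first 6.
- Largest 1000 mg BID denominator: 6 under the protocol, 20 under the SAP.
- True DLT rate p: not in the documents, so 5% to 20% is assumed.
- Number evaluable at 1000 mg BID, n: not in the documents, so it is varied.

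**A simple case.** Suppose there is 1 DLT in the first 6 and 1 among later subjects. The protocol's set gives 1/6, which meets the rule. In the SAP's set:
- n = 7 to 11: fails on both readings (2/11 = 18.2%, above 1/6 = 16.7%).
- n = 12 to 20: fails as a count, passes as a proportion (2/12 = 16.7%; 2/20 = 10%).

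**How likely is a conflict?** Let X₆ ~ Bin(6, p) and Xₘ ~ Bin(n − 6, p). The chance that the level fails in the SAP's set after passing on its first 6 is

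P(X₆ + Xₘ ≥ k | X₆ ≤ 1) = [P(X₆=0)·P(Xₘ ≥ k) + P(X₆=1)·P(Xₘ ≥ k−1)] / P(X₆ ≤ 1).

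For the count reading k = 2. For the proportion reading k is the smallest integer with k/n > 1/6: 2 for n = 7–11, 3 for n = 12–17, 4 for n = 18–20.

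Worked for p = 0.10, n = 20:
- P(X₆=0) = 0.9⁶ = 0.5314; P(X₆=1) = 6 × 0.1 × 0.9⁵ = 0.3543; sum 0.8857.
- Count: (0.5314 × 0.4154 + 0.3543 × 0.7712) / 0.8857 = 0.4940 / 0.8857 = 0.558.
- Proportion: (0.5314 × 0.0441 + 0.3543 × 0.1584) / 0.8857 = 0.0796 / 0.8857 = 0.090.

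All 20 evaluable:

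| True DLT rate | P(first 6 pass) | Fails as count (≥2/20) | Fails as proportion (≥4/20) |
|---|---|---|---|
| 5% | 0.967 | 24% | 1% |
| 10% | 0.886 | 56% | 9% |
| 15% | 0.776 | 77% | 25% |
| 20% | 0.655 | 89% | 45% |

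Fewer evaluable (count / proportion):

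| n | True rate 5% | True rate 10% |
|---|---|---|
| 6 or fewer | 0% | 0% |
| 8 | 2.5% / 2.5% | 8% / 8% |
| 10 | 5.5% / 5.5% | 17% / 17% |
| 12 | 9% / 1% | 26% / 6% |
| 15 | 14% / 2% | 38% / 12% |

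Under the protocol's definition the chance is 0% by construction, because only the first 6 count.

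**The case against.** The strongest reply is that little may turn on this.

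- **Enrolment is unknown.** The study stopped during Phase 1b, and with six or fewer evaluable subjects at 1000 mg BID the two definitions coincide. This stands: the size is conditional.
- **The count reading is the less natural one for 20 subjects.** SAP 1.2.1 separates the initial six from the additional 14 and sends later subjects to the MTD if more than one of the first six has a DLT. A careful reader could infer the protocol's intent. That lowers the risk but does not repair 3.1.4, which names the set for the MTD without the limit. With 7 to 11 evaluable, the two readings give the same failure risk.
- **The true rate may be low.** Protocol 1.4 reports no clinically meaningful safety findings up to 1000 mg, and termination was for lack of efficacy. This does not establish the rate at 1000 mg BID, but it makes the 5% figures as relevant as the 10% ones.
- **Downstream use is limited.** The safety review team sets the MTD during the study, Phase 2 was not started, and the output is a synoptic report. This also stands, and confines the effect to reporting.
- **The protocol wording has its own gap.** It does not say whether replacements under protocol 4.1.2 count among the first six. That is worth settling in the same edit.
- **The protocol version cannot be confirmed.** The SAP cites amendment 5.0 and the title page of the supplied protocol was removed. The cohort text matches, so this is only a caveat.

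**Conclusion.** The concern holds. SAP 3.1.4 differs from the protocol on who counts at 1000 mg BID for the primary endpoint and the MTD. The only MTD rule is written for six, and SAP 7.7 says nothing changed. The effect is nil with six or fewer evaluable subjects at that level. Beyond six, the two definitions can give opposite MTD statements, with a probability that depends on assumed DLT rates, on the unreported enrolment and, from 12 subjects up, on which reading is used.

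The enrolment condition for the additional 14 and the decisions taken during the study are not affected. This should be fixed before the study report, but it does not threaten the study's conduct.

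**What to change.** 1. In SAP 3.1.4, restore the protocol's limit for the MTD determination: "up to the first 6 subjects in the 1000 mg BID dose escalation cohort". State whether replacement subjects count towards the six.
2. Correct SAP 7.7. If the wider set is intended, declare and justify it there, and state how the MTD rule applies to more than six subjects.
3. Restoring the limit removes Day 1–21 events in the seventh and later 1000 mg BID subjects from the DLT table in SAP 7.1.7. Those events stay in the TEAE tables, and SAP section 3 provides that "By-subject listings will be presented for all subjects in the All Enrolled Analysis Set". To keep them visible as DLT-criteria events, add one supportive Day 1–21 summary by dose level in the Safety Analysis Set, and state that the DLT listing covers all treated subjects. Neither document requires this table; it is a recommended complement.

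The cost is wording in 3.1.4, 7.1.7 and 7.7 plus one table from adverse event data already collected, with no change to study conduct. The SAP carries July 2021 signatures. If it is already final, its Introduction provides for recording later changes in the study report.
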